### **2.5.2.3. Medical History**

The number and percentage of participants with any medical history will be summarized by SOC and PT based on the Safety Set. A participant will be counted only once for multiple events within each SOC and PT. SOC will be displayed in internationally agreed order. PT will be displayed in descending order of frequency of the mRNA-1345 (█  $\mu$ g) + Afluria Quadrivalent group and then alphabetically within SOC.

Number of events and number of participants with selected medical conditions, as indicated in [Appendix K, Table 17](#), will also be summarized by SOC, HLTG, and PT for each vaccination group.

The number and percentage of participants with any medical history will be also summarized by SOC and PT based on the Supportive PP Set and presented by the vaccination group as indicated in [Section 2.5.2.2](#). PT will be displayed in descending order of frequency of the “Adjusted Group 1” and then alphabetically within SOC.

Medical history data will be coded by SOC, HLTG (for selected medical conditions), and PT according to the MedDRA (Version 25.0 or higher).

### **2.5.2.4. Prior and Concomitant Medications**

Prior medications (including any prescription or over-the-counter medications, vaccines, or blood products) taken by the participant within the 28 days before providing informed consent will be recorded in the participant’s eCRF. Medications and non-study vaccinations taken/received by the participant during the study will be recorded in the eCRF for the information as specified in Section 2.5.5.2 of the study protocol. Prior and concomitant medications will be coded using the WHO-DD. The summary of concomitant medications will be based on the Safety Set. Imputation rules for missing/partial dates for medications is detailed in [Appendix C](#).

For the purpose of analysis, a medication taken prior to the injection date, regardless of whether the end date is before or after the injection date, is defined as “prior”; if the medication is taken between the injection date and up to 28 days after the injection date (inclusive), then it is

considered “concomitant”, regardless of whether the start date is before or after the injection date; if the medication is taken after 28 days post injection (i.e. end date of the medication is after 28 days post injection or ongoing after 28 days after IP injection), it is a “post” medication.

An overall summary table of concomitant medications and non-study vaccinations will be provided to present the number and percentage of participants who take the following:

- Any concomitant medications and non-study vaccinations within 7 days post injection
- Any concomitant medications and non-study vaccinations within 28 days post injection
- Any non-study vaccinations within 7 days post injection
- Any non-study vaccinations within 28 days post injection
- Any prophylactic antipyretics or analgesics medication within 28 days post injection
- Any antipyretic or analgesic medication within 28 days post injection

A summary table of concomitant medications and non-study vaccinations within 28 days post injection will be provided by ATC level 2 and preferred term. Preferred terms will be displayed in descending order of frequency of the mRNA-1345 (C1  $\mu$ g) + Afluria Quadrivalent group. A separate summary table of non-study vaccinations within 7 days post injection will be also provided by preferred term.

An overall summary of medications taken to prevent or treat fever or pain within 7 days post injection will be also provided based on Solicited Safety Set. The summary will be based on participants’ responses to the eDiary questions regarding whether they have taken any antipyretic or analgesic medications to prevent or treat fever/pain within 7 days post injection.

Prior, concomitant and post medications and non-study vaccinations will be presented in a listing.

#### **2.5.2.5. Concomitant Procedures/Surgeries**

Procedures and/or surgeries data will be coded by SOC and PT using the MedDRA. Imputation rules for missing/partial dates of procedures/surgeries are detailed in [Appendix D](#).

For the purpose of analysis, a procedure/surgery occurred prior to the injection date (including cases where the procedure/surgery date is completely missing) is defined “prior”; if the procedure/surgery is performed on or after the injection date and on or prior to 28 days after the injection date, then it is considered “concomitant”; otherwise, it is a “post” procedure/surgery.

The number and percentage of participants with any concomitant procedure/surgery will be summarized by SOC and PT based on the Safety Set. A participant will be counted only once for multiple procedures/surgeries within each SOC and PT. SOC will be displayed in internationally agreed order. PT will be displayed in descending order of frequency of the mRNA-1345 (█  $\mu$ g) + Afluria Quadrivalent group and then alphabetically within SOC.

Concomitant and post procedures/surgeries will be presented in a listing.

#### **2.5.2.6. Study Exposure**

Summary of time on study in days will be presented by vaccination group in Safety Set, PP Set and Supportive PP Set for the following:

- Time on study from randomization in days: calculated as date of study discontinuation/completion – date of randomization +1.
- Time on study from injection in days: calculated as date of study discontinuation/completion – date of Day 1 injection +1.

In the Supportive PP Set, the duration will be presented by the vaccine group as indicated in [Section 2.5.2.2](#). The number and percentage of participants of receiving initial mRNA-1345 in each calendar month (April-2022, May-2022, and June-2022) will also be provided.

Study injection detail as well as participant with dosing error will be also presented in a listing.

#### **2.5.2.7. Significant Protocol Deviations**

Significant protocol deviations are a subset of protocol deviations that may significantly impact the completeness, accuracy, or reliability of the study data or that may significantly affect a participant's rights, safety, or well-being. Significant protocol deviations rules will be developed based on the protocol and ongoing data, and will be finalized before DBL.

The number and percentage of the participants with each significant protocol deviation type will be provided by vaccination group on the Randomization Set.

Selected significant protocol deviations impact critical or key study data (also referred to as major protocol deviations in the protocol), and participants with such deviations will be excluded from the PP Set for immunogenicity analyses; such major protocol deviations will be determined and documented by Sponsor prior to DBL and unblinding. Reasons of exclusion from PP Set for immunogenicity will be summarized.

### **2.5.2.8. COVID-19 Impact**

An individual data listing on COVID-19 impact will be provided for the Randomization Set and it will include which visit(s)/assessment(s) has (have) been missed due to COVID-19, along with the specific relationship to COVID-19.

### **2.5.3. Safety Analysis**

Safety and reactogenicity will be assessed by clinical review of all relevant parameters including solicited ARs (local and systemic), unsolicited AEs, SAEs, MAAEs, AESI, AEs leading to study discontinuation, vital signs, and physical examination findings. Solicited ARs will be coded according to the MedDRA for AR terminology and unsolicited AEs will be coded by SOC and PT according to the MedDRA. The Toxicity Grading Scale for Healthy Adult and Adolescent Volunteers Enrolled in Preventative Vaccine Clinical Trials ([DHHS 2007](#)) will be used in this study.

All safety analyses will be based on the Safety Set, except summaries of solicited ARs, which will be based on the Solicited Safety Set. All safety analyses will be provided by vaccination group as defined in [Section 2.5.1](#), unless otherwise specified.

#### **2.5.3.1. Solicited Adverse Reactions**

An AR is any AE for which there is a reasonable possibility that the test product caused the AE. The term “Solicited Adverse Reactions” refers to selected signs and symptoms occurring after injection administration during a specified post-injection follow-up period (day of injection and 6 subsequent days). The solicited ARs are recorded by the participant in eDiary. The eDiary will solicit daily participant reporting of ARs using a structured checklist (Section 2.7.1.1 of the study protocol). Participants will record such occurrences in an eDiary from Day 1 through Day 7 (i.e., the day of injection and 6 subsequent days). Local solicited ARs will be recorded separately for each injection site (left and right arm). Severity grading of reactogenicity will occur automatically based on participant entry in the eDiary according to the grading scales presented in Table 4 of the study protocol from the toxicity grading scale for healthy adult and adolescent volunteers enrolled in preventive vaccine clinical trials ([DHHS 2007](#)).

If a participant had a Grade 1 or higher AR during the solicited period and did not record the event in the eDiary, the event should be recorded on the Reactogenicity eCRF. If the event starts during the solicited period, but continues beyond 7 days after dosing, the participants should notify the site to provide an end date and close out the event on the Reactogenicity eCRF. If the participant reported an event that started after the solicited period (i.e., after Day 7), it should be recorded as an AE on the AE eCRF.

The following local ARs for each injection site (left and right arm) will be solicited by the eDiary: injection site pain, injection site erythema (redness), injection site swelling/induration (hardness), and axillary (underarm) swelling or tenderness ipsilateral to the injection arm. The following systemic ARs will be solicited by the eDiary: headache, fatigue, myalgia (muscle aches all over the body), arthralgia (aches in several joints), nausea/vomiting, chills, and fever.

All solicited ARs (local and systemic) will be considered causally related to injection.

All analyses of solicited ARs will be provided by vaccination group as defined in [Section 2.5.1](#) based on the Solicited Safety Set. Summaries of local solicited ARs will be also presented by vaccination group and injection content (mRAN-1345, Afluria Quadrivalent, and Placebo).

The number and percentage of participants with any solicited ARs, any solicited local ARs and any solicited systemic ARs during the 7-day follow-up period after injection will be summarized by vaccination group with a 2-sided 95% exact CI using the Clopper-Pearson method. Refer to Safety Estimand 4a in [Appendix I, Table 9](#).

The following summaries for solicited ARs will be presented by vaccination group:

- The number and percentage of participants who reported each individual solicited AR (has a severity grade of Grade 1 or greater) during the 7-day follow-up period after injection will be summarized by severity grade. For each local solicited AR, the summary will be based on the highest grade of the ARs observed from both injection sites (left and right arm).
- The number and percentage of participants who reported each individual solicited AR will be summarized by the onset day relative to the injection (Day 1 through Day 7). The onset day of an individual solicited AR is defined as the time point after injection at which the respective solicited AR first occurred. For each local solicited AR, the summary will be based on the earliest onset day of the ARs from both injection sites (left and right arm).
- The duration (days) of each solicited AR will be summarized descriptively. The duration will be calculated as: end date of solicited AR event – reaction start date of solicited AR event +1, no matter if it is intermittent or continued or if the solicited AR continues beyond 7 days. For each local solicited AR, the summary will be based on the longest duration of the ARs observed from both injection sites (left and right arm).
- The number and percentage of participants who reported any solicited ARs that continue beyond 7 days post-injection will be summarized.

The number and percentage of participants who reported each individual solicited AR summarized by severity grade and by onset day will be also presented separately for local solicited ARs only by vaccination group and injection content.

Bar plots may be created to display the percentage of participants who reported solicited AR.

The summaries of solicited ARs by vaccination group and local solicited ARs by vaccination group and injection content may be provided for the following subgroup:

- Age group (50 to 59 years, 60 to 74 years,  $\geq$  75 years)
- Age group (50 to 59 years,  $\geq$  60 years)
- Sex (male, female)
- Race (White, Black, Asian, or other [including American Indian or Alaska Native, Native Hawaiian or other Pacific Islander and other races])

These summaries may be provided for additional subgroups of selected baseline characteristics.

#### **2.5.3.2. Adverse Events**

An AE is defined as any untoward medical occurrence in a clinical trial participant administered a medicinal drug product and which does not necessarily have a causal relationship with this treatment. AEs will also be evaluated by the investigator for the coexistence of MAAE which is defined as an AE that leads to an unscheduled visit to an HCP.

A TEAE is defined as any event occurring during the study not before exposure to study vaccine. Worsening of a pre-existing condition after vaccination will be reported as a new AE.

An unsolicited TEAE is any AE reported by the participant that is not specified as a solicited AR in the protocol or is specified as a solicited AR but starts outside the protocol-defined period for reporting solicited ARs (i.e., 7 days after study vaccine administration). For analysis and reporting purpose, unsolicited TEAEs will include the following:

- TEAEs that are reported by participants and recorded on the AE eCRF
- Solicited ARs that meet SAE criteria and are recorded on the Reactogenicity eCRF

Unsolicited AEs will be collected for up to 28 days after injection; SAEs, MAAEs, AESIs, and AEs leading to study discontinuation will be collected throughout the study. Unsolicited TEAEs will be summarized up to 28 days after injection unless otherwise specified. Additionally, SAEs, MAAEs, AESIs and AEs leading to study discontinuation will be summarized throughout the study (up to Day 181/EoS). Refer to Safety Estimand 4b in [Appendix I, Table 10](#).

All summary tables (except for the overall summary of TEAEs) for unsolicited TEAEs will be presented by SOC and PT (or by PT). SOC will be displayed in internationally agreed order. PTs will be displayed in descending order of frequency in the mRNA-1345 (█  $\mu$ g) + Afluria Quadrivalent group and then alphabetically within SOC. When summarizing the number and percentage of participants with an event, participants with multiple occurrences of the same AE or a continuing AE will be counted once.

For the by severity summaries, the toxicity grade of a solicited AR meeting SAE criteria after injection will be mapped to a severity level of Mild/Grade 1, Moderate/Grade 2 or Severe/ $\geq$  Grade 3 and the maximum severity level in the case of multiple events will be presented.

Percentages will be based upon the number of participants in the Safety Set within each vaccination group.

The number of events and number of participants reported occurrence of selected TEAEs of clinical interests identified by SMQs in up to 7 days post-injection, up to 28 days post-injection, and up to EoS will be summarized by SMQ, subordinate SMQ, and PT. Two sets of summary tables will be provided, one will be based on combined broad and narrow scope of SMQ, the other will be based on narrow scope. SMQ and subordinate SMQ within each SMQ will be displayed in alphabetic order. PT will be displayed in descending order of number of participants in mRNA-1345 (█  $\mu$ g) + Afluria Quadrivalent group and then alphabetically within subordinate SMQ or SMQ if no subordinate SMQ. Detail information for the selected SMQ is presented in [Appendix J Table 15](#) and [Table 16](#).

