#### 2.7.4.3. **Solicited Adverse Reactions**

The term “reactogenicity” refers to the occurrence and intensity of selected signs and symptoms (ARs) occurring after administration of the IP. The eDiary will solicit daily participant reporting of ARs using a structured checklist ([Section 2.7.1.1](#)). Participants will record such occurrences in an eDiary from the day of injection and 6 subsequent days). Local solicited ARs will be recorded separately for each injection site.

Severity grading of reactogenicity will occur automatically based on participant entry in the eDiary according to the grading scales presented in [Table 4](#) from the toxicity grading scale for healthy adult and adolescent volunteers enrolled in preventive vaccine clinical trials ([DHHS 2007](#)).

If a participant reported a solicited adverse reaction during the solicited period and did not record the event in the eDiary, the event should be recorded on the Reactogenicity page of the eCRF. If the event starts during the solicited period, but continues beyond 7 days after dosing, the participants should notify the site to provide an end date and close out the event on the

Reactogenicity page of the eCRF. If the participant reported an event that started after the solicited period, it should be recorded as an AE on the AE page of the eCRF. All solicited ARs (local and systemic) will be considered causally related to dosing.

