Abbreviations: AE = adverse event; eCRF = electronic case report form.

Note: Events listed in the table above but starting >7 days after study injection will be recorded on the AE page of the eCRF. Causality for each event will be determined per assessment by the investigator.

Source: Guidance for Industry – Toxicity Grading Scale for Healthy Adult and Adolescent Volunteers Enrolled in Preventive Vaccine Clinical Trials ([DHHS 2007](#)).

Any solicited AR that meets any of the following criteria must be entered into the participant's source document and must also be recorded by the study site staff on the solicited AR page of the participant's eCRF:

- Solicited local or systemic AR that results in a visit to a healthcare practitioner (HCP), to be recorded as an MAAE ([Section 2.7.4.4](#)).
- Solicited local or systemic AR leading to the participant withdrawing from the study or the participant being withdrawn from the study by the investigator (AE leading to withdrawal).
- Solicited local or systemic AR lasting beyond 7 days post-injection.
- Solicited local or systemic AR that otherwise meets the definition of an SAE.

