## **2.2. Study Endpoints**

### **2.2.1. Primary Endpoints**

#### **2.2.1.1. Primary Safety Endpoints**

The primary safety objective will be evaluated by the following safety endpoints:

- Numbers and percentages of participants with solicited local and systemic ARs over the 7 days post-injection
- Numbers and percentages of participants with unsolicited AEs through 28 days post-injection
- Numbers and percentages of participants with MAAEs, SAEs, AESIs, and AEs leading to withdrawal from Day 1 (baseline) to Day 181/EoS

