#### 2.5.3.2.1. Overview of TEAEs

Overall summary of unsolicited TEAEs up to 7 days post-injection, between 8 to 28 days post-injection, and up to 28 days post-injection will be provided, for the number and percentage of participants, along with the number of events, by vaccination group who experience at least one of the categories:

- Any unsolicited TEAEs
- Any serious TEAEs
- Any fatal TEAEs
- Any unsolicited medically-attended TEAEs
- Any unsolicited TEAEs leading to study discontinuation
- Any unsolicited severe TEAEs
- Any unsolicited non-serious TEAEs (no SAE)

- Any unsolicited non-serious severe TEAEs (no SAE)
- Any unsolicited non-serious TEAEs (regardless of SAE)
- Any unsolicited non-serious severe TEAEs (regardless of SAE)
- Any unsolicited AESI

Note: Severe TEAEs include both unsolicited severe TEAEs and  $\geq$  Grade 3 solicited ARs that meet SAE criteria after injection.

Summary tables will also be provided to include number and percentage of participants with unsolicited treatment-related TEAEs up to 28 days post-injection. Additionally, the overall summary for the categories of SAEs, MAAEs, AESIs, and AEs leading to study discontinuation will be provided for these TEAEs throughout the study. Separate listings containing individual participant AE data up to EoS for unsolicited TEAEs, serious TEAEs, unsolicited medically-attended TEAEs, unsolicited AESIs, unsolicited TEAEs leading to study discontinuation, severe TEAEs, fatal unsolicited TEAEs, and unsolicited AESIs will be provided.

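### The SAP leaves non-serious solicited reactions that led to a medical visit or withdrawal out of the MAAE and discontinuation overview, 28-day tables and listings, although the primary safety endpoint is not limited to unsolicited events

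*SAP*

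**What the plan says.** **Protocol 2.7.4.3** (text after Table 4) lists four kinds of solicited AR that "must also be recorded by the study site staff on the solicited AR page of the participant's eCRF". The first is a "Solicited local or systemic AR that results in a visit to a healthcare practitioner (HCP), to be recorded as an MAAE". The second is a "Solicited local or systemic AR leading to the participant withdrawing from the study" (or being withdrawn by the investigator), which the protocol labels an AE leading to withdrawal. The third is a reaction lasting beyond 7 days. The fourth is a "Solicited local or systemic AR that otherwise meets the definition of an SAE". The first two carry no seriousness condition.

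**SAP 2.5.3.2** builds unsolicited TEAEs from two sources: events on the AE eCRF, and "Solicited ARs that meet SAE criteria and are recorded on the Reactogenicity eCRF".

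**SAP 2.5.3.2.1** has an overview row for "Any unsolicited medically-attended TEAEs" and a matching unsolicited row for study discontinuation. The corresponding listings are also restricted to unsolicited events. The through-study overview refers back to the same TEAEs.

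**SAP 2.5.3.2.2** keeps the word unsolicited in the 28-day MAAE and discontinuation tables, but drops it from the tables that run through the whole study.

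**SAP 2.2.1.1** defines the Part A primary safety endpoint as "Numbers and percentages of participants with MAAEs, SAEs, AESIs, and AEs leading to withdrawal from Day 1 (baseline) to Day 181/EoS". The Part B and Part C endpoints (SAP 3.2.1.1 and 4.2.1.1) likewise have no limit to unsolicited events. SAP 3.5.3.2 and 4.5.3.2 take over the Part A rule by cross-reference, and the differences they list do not alter it.

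**The concern.** MAAEs and AEs leading to withdrawal or discontinuation are primary safety endpoints in all three parts, and the inclusion rule is narrower than the endpoint. The events at risk are reactogenicity events, the kind on which coadministration might plausibly differ from single vaccination. Every solicited AR is also treated as causally related to injection (protocol 2.7.4.3, SAP 2.5.3.1), so an omitted medically attended reaction is also missing from the 28-day table of treatment-related MAAEs.

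SAP Section 1 says that the SAP prevails where its methods differ from the protocol, and SAP Section 5 does not list this narrowing among its changes. A reader of the report would have no signal that the MAAE row excludes a class of events that the protocol calls MAAEs.

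**Working it through.** This is mainly a comparison of text. First, the protocol's four criteria against their place in the SAP:

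| Solicited AR that… | Protocol class | Place in the SAP |
|---|---|---|
| leads to an HCP visit | MAAE | none stated if non-serious |
| leads to withdrawal | AE leading to withdrawal | disposition reason only, if non-serious |
| lasts beyond 7 days | none given | own summary in SAP 2.5.3.1 |
| meets the SAE definition | SAE | counted with unsolicited TEAEs |

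Two of the four have a stated route into the safety event analysis. The first two do not unless they are also serious.

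Next, trace one case: a headache starting on Day 3 that leads to a same-day emergency room visit.

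1. Protocol Table 4 grades it 4. The hospitalization criterion in protocol 2.7.4.2 generally means at least one overnight stay, so the event need not be an SAE.
2. It belongs on the solicited AR page. Protocol 2.7.4.3 sends solicited-type events to the AE page when they start after the solicited period. For a reaction inside the period that was missed in the eDiary, it says "the event should be recorded on the Reactogenicity page of the eCRF".
3. Under SAP 2.5.3.2 it is not an unsolicited TEAE: it is a solicited term starting inside the 7-day period, it is not on the AE page, and it is not an SAE.
4. It is therefore absent from the MAAE overview row, the 28-day MAAE tables, the MAAE listing and the through-study overview.
5. Whether it enters the through-study MAAE table by system organ class is not stated.
6. It does appear in the solicited AR tables. Those report grade, onset day, duration and persistence, not medical attendance or withdrawal.

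For scale only, the formulas are expected number = n × p and P(at least one) = 1 − (1 − p)^n. The second reproduces the plan's own figures:

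- n = 420, p = 0.7%: 94.8% (stated 95%)
- n = 600, p = 0.5%: 95.1% (stated 95%)
- n = 560, p = 0.5%: 94.0% (stated 94%)
- n = 500, p = 0.5%: 91.8% (stated 92%)

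The documents give no rate for non-serious solicited ARs with an HCP visit or withdrawal. **Assuming** 0.1% to 1%:

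| Planned n | Expected omitted | P(at least one) |
|---|---|---|
| 600 (Part A, Groups 2 and 3) | 0.6 to 6 | 45% to 99.8% |
| 560 (each Part B group) | 0.56 to 5.6 | 43% to 99.6% |
| 500 (Part C) | 0.5 to 5 | 39% to 99.3% |

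After the IRT error in SAP 2.3.4, Part A Group 2 is nearer (1620 − 250)/2 = 685, which gives 0.7 to 6.9.

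**The case against.** The strongest reply is that the two source bullets define only unsolicited TEAEs. In SAP 2.5.3.2 a TEAE is any event not before exposure, and an MAAE is any AE leading to an unscheduled HCP visit. On those definitions a medically attended solicited AR is an MAAE. The through-study tables in SAP 2.5.3.2.2, which match the endpoint's time frame, omit the word unsolicited and cover all events reported. This stands in part: those tables could be programmed to include the missing events. But no text says so, and they would then disagree with the overview and listings in SAP 2.5.3.2.1.

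A second reply is that recording a reaction as an MAAE may mean a further entry on the AE page, which would bring it in through the first bullet. That is possible, and the eCRF itself is not available to settle it. No section says it, however. Protocol 2.7.4.4 describes MAAE review for unsolicited AEs only, and the SAP's definition of unsolicited excludes solicited terms starting inside the window. If only some sites enter events twice, the counts would depend on site practice.

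A third reply is that nothing is hidden, and this is largely right. Solicited ARs are themselves a primary safety endpoint and are tabulated by grade. For pain, axillary reactions and most systemic reactions, Grade 4 means an emergency visit or hospitalization. Disposition gives withdrawal reasons by group, and a solicited AR is a listed reason in protocol 2.6.2. What is lost is the events' status as MAAEs or AEs leading to discontinuation. One side effect is that disposition could show a withdrawal for a solicited AR that the discontinuation table lacks.

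**Conclusion.** The gap in the rule is real. As written, non-serious solicited ARs that were medically attended or caused withdrawal are left out of the MAAE and discontinuation overview, 28-day tables and listings, unless sites also enter them on the AE page. The overview and the through-study tables by system organ class can disagree. Serious solicited ARs are captured.

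A reader might infer two stronger conclusions, and the documents support neither:

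- **That the primary endpoint is demonstrably undercounted.** The wording of the through-study tables leaves room to include these events, a second AE-page entry is not ruled out, and with no rate given the number may be small or zero. The 0.6 to 6 per 600 rests wholly on the assumed 0.1% to 1%.
- **That the rule favours coadministration.** That holds only if coadministration proves more reactogenic in this respect, which the documents do not establish.

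The point still merits a change, because it concerns a primary safety endpoint and the correction uses data that sites are already required to record.

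**What to change.** Leave the SAP 2.5.3.2 definition of unsolicited TEAE unchanged. Widening its second bullet would put non-serious solicited ARs into every unsolicited table and so alter another primary endpoint, unsolicited AEs through 28 days.

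Instead, in SAP 2.5.3.2.1 and 2.5.3.2.2:

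- Build the MAAE, treatment-related MAAE and AE-leading-to-discontinuation tables and listings from both the AE and Reactogenicity eCRF pages.
- Count each event once, so that an event entered on both pages is not doubled.
- Drop the word unsolicited from those titles and rows.
- Carry the rule to Parts B and C, and record it in SAP Section 5.

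The cost is an SAP clarification and some table programming. MAAE and discontinuation rates may rise slightly.
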